6.1 Study Intervention(s) Administration

Study Intervention(s) Administered

Intervention Name	M5717	Pyronaridine tetraphosphate	Atovaquone – proguanil hydrochloride
Intervention Description	On Day 1 participants will receive a single dose of M5717 of either 60, 200, or 660 mg in loose combination with a single dose of pyronaridine	On Day 1 participants will receive a single dose of 720 mg (participants ≥ 65 kg) or 540 mg (participants ≥ 45 to < 65 kg) pyronaridine irrespective of the dose of M5717	Participants in Cohort 4 will receive 3 doses of atovaquone – proguanil on Days 1, 2, and 3
Type	Drug	Drug	Drug
Dose Formulation	Capsules* (containing granules to be dispersed in water) *M5717 dose formulation is capsules, containing granules to be dispersed in water; it is also referred as hard capsules or sprinkle capsules.	Tablet	Tablet
Unit Dose Strength(s)	100 mg capsules, 30 mg capsules	180 mg tablets	250/100 mg fixed-dose combination
Dose	60 mg, 200 mg, 660 mg	720 mg, 540 mg	1,000/400 mg
Dosage Regimen	1 day treatment regimen	1-day treatment regimen	3-day treatment regimen (4 tablets per day)
Route of Administration	Oral, fasting condition	Oral, fasting condition	Oral
Use	Experimental	Experimental	Control
IMP or NIMP/AxMP	IMP	IMP	IMP
Sourcing	M5717 will be provided by the Sponsor	Pyronaridine to be supplied by Shin Poong Pharmaceuticals	Atovaquone proguanil will be provided by the Sponsor; sourced via qualified vendor/CDMO.
	CCI		

M5717
MS201618_0034

**Efficacy, Safety, and PK of M5717-Pyronaridine as Chemoprevention in Adults and Adolescents
with Asymptomatic *Plasmodium falciparum* Infection**

Intervention Name	M5717	Pyronaridine tetraphosphate	Atovaquone – proguanil hydrochloride
Current/Former Name(s) or Alias(es)	M5717: MSC2576186A		Atovaquone-proguanil; Malarone

Study Arm(s)

Arm Name	Single dose 60 mg M5717 plus 720 mg (participants \geq 65 kg) or 540 mg (participants \geq 45 to < 65 kg) pyronaridine	Single dose 200 mg M5717 plus 720 mg (participants \geq 65 kg) or 540 mg (participants \geq 45 to < 65 kg) pyronaridine (Cohort 2)	Single dose 660 mg M5717 plus 720 mg (participants \geq 65 kg) or 540 mg (adolescents) pyronaridine (participants \geq 45 to < 65 kg) (Cohort 3)	3 doses of 1,000 mg/ 400 mg atovaquone – proguanil on 3 consecutive days (Cohort 4)
Arm Type	Experimental	Experimental	Experimental	Control

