6.7 Treatment of Overdose

For this study, any dose greater than the highest daily dose included in a clinical study protocol or planned for an individual participant enrolled in the study will be considered an overdose.

Even if not associated with an AE, SAE, or AESI, any overdose is recorded in the CRF and reported to global patient safety in an expedited manner. Overdoses are reported on an SAE and Overdose Report Form, following the procedure in [Appendix 5](#).

The effects of a M5717 overdose are unknown, and therefore no standard treatment is currently established. In the event of an overdose, the Investigator or treating physician should use appropriate clinical judgment for the evaluation and management of any clinical signs, symptoms, and laboratory results.

No case of overdosage with Pyramax has been reported. In cases of suspected overdosage symptomatic and supportive therapy should be given as appropriate, and transaminases (AST and ALT) should be monitored. If there are significant rises, then serial total and direct bilirubin values should also be obtained to determine whether there is any change in liver function.

There is insufficient experience to predict the consequences or suggest specific management of Malarone overdose. However, in the reported cases of atovaquone overdose, the observed effects were consistent with known undesirable effects of the drug ([SmPC Malarone](#)). If overdose occurs, the participant should be monitored, and standard supportive treatment applied.

Refer to package inserts of the rescue medication for details regarding the effects and management of an overdose.

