15.1.2 The 3-Tier Approach

The 3-tier approach for summarizing and analyzing AEs in clinical studies will be followed. AEs in different tiers are analyzed using different types of statistical analysis.

The AEs identified for Tier 1 reporting are listed in below table together with the description how Tier 1 AEs will be analyzed:

Tier 1 AE	Within group summary	Between group comparison (Each dose cohort – natural infection cohort) 95% CI
Nervous system disorders (SOC 10029205)	n (%)	Δ [xx%, xx%]
ALT increased (PT 10001551)		
ALT abnormal (PT 10001547)		
AST increased (PT 10003481)		
AST abnormal (PT 10003477)		
AST/ALT ratio abnormal (PT 10082832)*		

* either documented AE or AST/ALT=abnormal in laboratory data. An AST/ALT ratio between 0.7 and 1.4 is thereby interpreted as “normal”. Values outside of this range are “abnormal”.

All Tier 1 events will be summarized in a table. Incidence rates and differences in incidence rates between each dose cohort and the natural infection cohort will be provided together with 95% CIs for the differences in incidence rates. For Tier 1 events which were observed for less than 3 participants the CIs will not be displayed in the Tier 1 table. 95% CIs for the differences in incidence rates will be estimated using Miettinen & Nurminen method. For graphical illustration a forest plot will be provided separately for the different treatment cohorts.

All TEAEs for which any PT or SOC is observed in 4 or more participants in any cohort are defined to be Tier 2 AEs. Tier 2 AEs are thus used for signal detection among common events. A frequency table by SOC and PT will be provided together with differences in incidence and 95% CI comparing different dose groups to the natural infection cohort. While analyses will be done for all Tier 2 TEAEs, only TEAEs with incidence proportion $\geq 5\%$ in at least one cohort will be presented in the body of CSR. No multiplicity adjustment will be applied.

Remaining TEAEs are defined as TIER 3 AEs and frequencies of participants with at least one Tier 3 TEAE will be provided by SOC and PT.

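### Tier 1 and Tier 2 safety contrasts are planned only per dose cohort; a supplementary contrast of pooled Cohorts 1 to 3 with Cohort 4 would bound shared liver harm more tightly.

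*SAP*

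**What the plan says.** **Contrasts.** In SAP 15.1.2, Tier 1 covers nervous system disorders and the ALT and AST terms. For these: "Incidence rates and differences in incidence rates between each dose cohort and the natural infection cohort will be provided together with 95% CIs". On method: "95% CIs for the differences in incidence rates will be estimated using Miettinen & Nurminen method". On display: "For Tier 1 events which were observed for less than 3 participants the CIs will not be displayed in the Tier 1 table". The forest plot is separate for each cohort. Tier 2, for events seen in at least four participants of any cohort, gives "differences in incidence and 95% CI comparing different dose groups to the natural infection cohort", and that paragraph adds: "No multiplicity adjustment will be applied".

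**Layout.** SAP 9.3 presents tables and figures by treatment group. An overall presentation is named only for disposition (SAP 10.1). No visible text pools Cohorts 1 to 3 for safety. Parts of the SAP are blacked out, and the table shells are not among the documents.

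**Exposure.** Protocol 6.1 gives 720 or 540 mg by weight band of "pyronaridine irrespective of the dose of M5717". M5717 itself is a "single dose of M5717 of either 60, 200, or 660 mg". Protocol 6.3.1 allocates 1:1:1:1, stratified by site. Protocol 9.2 plans 192 randomised and 45 evaluable per cohort. The safety set takes everyone dosed, so up to 48 per cohort.

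**The concern.** Safety of the combination is a secondary objective. Liver events are an adverse event of special interest (Protocol 8.3.6) and a stopping criterion that counts participants without splitting them by cohort (Protocol 4.1). The overdose section says of Pyramax, which contains pyronaridine, that "transaminases (AST and ALT) should be monitored" (Protocol 6.7). The monitoring committee may recommend changes to the pyronaridine dose (Protocol 6.5), the component common to Cohorts 1 to 3.

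A reader will therefore ask whether the combination raises transaminases at whatever M5717 dose it is given. The planned contrasts answer only with about 48 against 48 participants, one third of the 144 exposed. Harm that does not depend on M5717 dose would be estimated three times, each time less precisely than the collected data allow.

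**Working it through.** **Inputs.** Cohort size 192/4 = 48 (safety set, at most) or 180/4 = 45 (evaluable); pooled 144 or 135; Cohort 4 stays at 48 or 45. The plan gives no expected liver event rate and no safety precision figure, so there is none to reproduce. All event counts and rates below are assumptions.

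**Method.** The Miettinen-Nurminen limits are the values d at which

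T(d) = (x1/n1 − x2/n2 − d) / sqrt{ [p1(1−p1)/n1 + p2(1−p2)/n2] · N/(N−1) } = ±1.96,

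with p1 and p2 the maximum likelihood estimates under p1 − p2 = d, and N = n1 + n2.

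**Step 1: no events.** The upper limit solves d/(1−d) = 3.84·N/[n1(N−1)].
- 48 v 48: 3.84 × 96/(48 × 95) = 0.081, so d = 7.5 points.
- 144 v 48: 3.84 × 192/(144 × 191) = 0.027, so d = 2.6 points.

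The ratio of upper limits is 2.86. The lower limits barely differ (−7.5 and −7.4), so the whole interval is 15.0/10.1 = 1.49 times as wide.

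**Step 2: three or more events per dose cohort, same rate in each.** Upper limits in percentage points:

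| Per cohort | Pooled | Upper, per cohort | Upper, pooled | Ratio |
|---|---|---|---|---|
| 3/48 v 0/48 | 9/144 v 0/48 | 16.9 | 11.5 | 1.47 |
| 3/48 v 1/48 | 9/144 v 1/48 | 15.1 | 9.9 | 1.53 |
| 3/48 v 3/48 | 9/144 v 3/48 | 11.6 | 6.8 | 1.70 |
| 5/48 v 2/48 | 15/144 v 2/48 | 18.7 | 13.3 | 1.40 |
| 5/48 v 5/48 | 15/144 v 5/48 | 13.4 | 8.6 | 1.55 |
| 9/48 v 5/48 | 27/144 v 5/48 | 23.2 | 18.0 | 1.29 |

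Whole intervals are 1.27 to 1.44 times as wide per cohort as pooled. The large-sample standard error ratio at equal rates is sqrt[(1/48 + 1/48)/(1/144 + 1/48)] = sqrt(1.5) = 1.22. The gain is limited because Cohort 4 does not grow.

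**Step 3: the display rule.** The SAP does not say whether fewer than three participants is counted per cohort or across cohorts. If per cohort, 2/48 in every dose cohort v 0/48 shows no interval, while pooled 6/144 v 0/48 would show −3.4 to 8.8 points. At an assumed 2% rate, the binomial chance of at least three events is 7% in 48 participants and 55% in 144.

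**Step 4: chance that an interval lies above zero.** Exact enumeration at 45 per cohort, with Cohort 4 shared. For at least one per-dose interval the chance is Σc P(C = c)·[1 − Π(1 − qi(c))], where C is the Cohort 4 event count and qi(c) is the chance that cohort i's lower limit exceeds zero given C = c.

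| Assumed risks (Cohorts 1, 2, 3 v 4) | One named cohort | At least one of three | Pooled |
|---|---|---|---|
| 15%, 15%, 15% v 2% | 63% | 87% | 77% |
| 10%, 10%, 10% v 1% | 48% | 74% | 57% |

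If only the 660 mg cohort carries the risk (2%, 2%, 15% v 2%), the chance is 63% for the 660 mg contrast and about 9% pooled. For 1%, 1%, 10% v 1% it is 48% and 1%.

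**The case against.** **The cohorts may not share one liver risk.** M5717 spans 660/60 = 11-fold, and no visible text shows that liver risk is independent of it. The overdose text concerns Pyramax and does not show this either. The safety objective is about different M5717 doses. This stands: the pooled row can only supplement the per-dose rows. A reader might infer that pooling should become the main reading for liver events; Step 4 shows that this could hide a risk confined to 660 mg.

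**A shared signal is not more likely to be missed per dose.** A reader might infer that three small contrasts would miss what one pooled contrast finds. Such a pattern can occur: 6/48 in every dose cohort v 1/48 gives three intervals from −0.1 to 23.0, while 18/144 v 1/48 gives 0.9 to 17.3. In the scenarios of Step 4, however, all three per-dose intervals fail to lie above zero in 13% and 26% of trials, against 23% and 43% for the pooled interval. Three looks also give more chances of a false positive, but that is a different matter.

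**The study is exploratory, and liver signals appear elsewhere.** Protocol 9.1 plans no confirmatory testing. SAP 15.2.5 adds an eDISH plot, individual laboratory plots and shift tables, and a reader can add up the cohort counts. This stands in part. None of these gives a combination-level risk difference with an interval, and in a descriptive study the interval is what the tables have to offer.

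**Conclusion.** The plan makes no combination-level safety contrast, although equal randomisation and a common pyronaridine rule allow one without weighting. The upper limit of the risk difference is about 1.3 to 1.7 times as large per cohort as it would be pooled. This assumes three or more events per dose cohort, equal risks across the three, and 48 dosed per cohort.

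A reader might take from the zero-event limits (7.5 v 2.6 points) that per-cohort intervals are almost three times as wide in general. They are not. That ratio belongs to the upper limit with no events, where the whole interval is about 1.5 times as wide and Tier 1 would normally not display it.

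This is a low-cost improvement in precision. The per-dose contrasts are sound and needed for dose-related harm.

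**What to change.** In SAP 15.1.2:
- Add a supplementary descriptive row or column, *all M5717 + pyronaridine* (Cohorts 1 to 3 pooled), to the Tier 1 and Tier 2 tables and the forest plot, with its risk difference against Cohort 4 and Miettinen-Nurminen 95% CI.
- Keep the per-dose rows unchanged and with the same standing. State that the pooled row is read together with them because it assumes a risk common to the three M5717 doses.
- Apply the fewer-than-three-participants rule to the pooled count for that row, and say how the rule is counted for the per-dose rows.

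This needs table programming only, with no new data and no change to planned analyses. The downside is dilution of an effect confined to one M5717 dose, which the per-dose rows still show.

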Adaptive Aspects of Study Design	
Safety stopping criteria:
 
If one of the criteria is met, the current study will be put on hold until it has been established that the benefit-risk of the combination is optimal
 
1. Liver toxicity signals: > 1 participant present any of the following criteria:
a. Presence of Hy's law criteria (ALT and/or AST > 3 × ULN, and elevation of serum TB to > 2 × ULN, without initial findings of cholestasis [elevated serum ALP], with no other reason to explain the combination of increased transaminases and TB).b. CTCAE v5.0 ≥ Grade 3 ALT or AST increases, that do not return to normality or below 1.5 × the ULN at the end of follow-up (28 days after first treatment).c. CTCAE v5.0 ≥ Grade 3 ALT or AST increases accompanied by posttreatment established coagulation disorder at any time (INR ≥ 1.5) not related to another underlying condition.2. CNS signals:
a. if ≥ 1 participant present persistent severe study intervention-related CNS disorders considered AEs that do not resolve within 2 weeks after the onset, orb. if ≥ 2 participants present persistent severe study intervention-related CNS AEs irrespectively of the recovery status, orc. if ≥ 1 participants experience a serious study intervention-related CNS AE.3. SUSAR Grade 4 or higher according to the CTCAE v5.0.
----------------------------------	---

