15.2.3 Other Significant Adverse Events

AEs of special interest (AESIs) include the following events as defined by the CTP:

- Liver events, monitored through LFTs that will include ATS, ALT, and AST, as well as TB and ALP
- Neurological events, monitored through specific neurological clinical examinations

AESIs will be identified by the corresponding flag on the AE page of the eCRF and by specifically search for them with an appropriate list of PTs. A frequency table of AESIs by SOC and PT will be provided.

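### The Tier 1 adverse event table drops the confidence interval of the risk difference when fewer than 3 participants have the event, and no other planned table is certain to supply it

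*SAP*

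**What the plan says.** SAP 15.1.2 names six Tier 1 items: the nervous system disorders SOC, four preferred terms (ALT increased, ALT abnormal, AST increased, AST abnormal) and an abnormal AST/ALT ratio, which may come from a reported event or from laboratory data. For all of them, "Incidence rates and differences in incidence rates between each dose cohort and the natural infection cohort will be provided together with 95% CIs", and the method is fixed: "95% CIs for the differences in incidence rates will be estimated using Miettinen & Nurminen method". One sentence makes an exception: "For Tier 1 events which were observed for less than 3 participants the CIs will not be displayed in the Tier 1 table". The SAP gives no reason for it and does not define how the participants are counted.

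The other outputs that might carry the interval are these:

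- **Tier 1 figure:** "For graphical illustration a forest plot will be provided separately for the different treatment cohorts". The SAP does not say whether the exception applies to it.
- **Tier 2:** "All TEAEs for which any PT or SOC is observed in 4 or more participants in any cohort are defined to be Tier 2 AEs". These get differences with 95% intervals.
- **Tier 3:** "Remaining TEAEs are defined as TIER 3 AEs and frequencies of participants with at least one Tier 3 TEAE will be provided". No interval is mentioned.
- **Adverse events of special interest (SAP 15.2.3):** "A frequency table of AESIs by SOC and PT will be provided". No interval is mentioned here either.

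**The concern.** Tier 1 is the sponsor's own list of prespecified events for comparison with the natural infection cohort. In a study of this size, counts of 0, 1 or 2 are likely for individual preferred terms. At those counts the point difference is close to zero and says little alone; the interval tells the reader how large an excess the data leave open. Under the present wording the table prints the difference and leaves the interval out.

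The undefined count is a second weakness in the same sentence. Two programmers could apply it differently and produce different tables from the same data.

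**Working it through.** **Inputs.** Protocol 9.2 randomises 192 participants 1:1:1:1, so 192/4 = 48 per cohort, and expects 180 evaluable, so 180/4 = 45. Safety analyses use all treated participants (SAP 8.1), so up to 48 apply; 45 is a check. The documents state no interval or expected rate for these events, so there is no figure of the plan to reproduce. The event rates below are assumptions.

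**Step 1: can the interval be calculated?** The Miettinen-Nurminen limits are the values D that solve

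(x1/n1 - x0/n0 - D)² = 3.841 × [N/(N-1)] × [p1(1-p1)/n1 + p0(1-p0)/n0],

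where N = n1 + n0, and p1 and p0 are the maximum likelihood estimates under p1 - p0 = D.

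For the upper limit with no event in Cohort 4, the restricted estimates are p0 = 0 and p1 = D. With e = x1/48 and k = 3.841 × (96/95)/48 = 0.0809, the equation becomes (e - D)² = k·D(1-D), which gives

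D = [(2e + k) + √((2e + k)² - 4(1 + k)e²)] / [2(1 + k)].

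- 0 v 0: D = k/(1 + k) = 0.0809/1.0809 = 7.5 points.
- 1 v 0 (e = 0.0208): D = (0.1225 + 0.1146)/2.1617 = 11.0 points.
- 2 v 0 (e = 0.0417): D = (0.1642 + 0.1395)/2.1617 = 14.0 points.

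The lower limits for 1 v 0 and 2 v 0 come from solving the same equation numerically. For 0 v 0 the interval is symmetric.

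| Dose cohort v Cohort 4 | Difference, 48 each | 95% CI, 48 each | 95% CI, 45 each |
|---|---|---|---|
| 0 v 0 | 0.0 | -7.5 to +7.5 | -7.9 to +7.9 |
| 1 v 0 | 2.1 | -5.5 to +11.0 | -5.8 to +11.6 |
| 2 v 0 | 4.2 | -3.5 to +14.0 | -3.7 to +14.9 |
| 3 v 0 | 6.3 | -1.5 to +16.9 | -1.5 to +17.9 |

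All values are percentage points. The first three rows fall under the exception on any reading of the count, provided no other cohort has events. The 3 v 0 row would be displayed. The method therefore works throughout, and the 2 v 0 interval is no wider than the 3 v 0 interval that would be printed.

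**Step 2: how often would the rule apply?** Assume a true rate of 5% in one dose cohort of 48.

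- *Per cohort:* P(X ≤ 2), X ~ Bin(48, 0.05), is 0.085 + 0.215 + 0.266 = 57%. At 4% it is 70%, and at 3% it is 83%.
- *Over all cohorts:* P(X + Y ≤ 2), with Y ~ Bin(144, q) for the other three cohorts, is 26% at q = 1% and 10% at q = 2%.

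The frequency therefore depends strongly on the definition that the SAP leaves open.

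**Step 3: does another table restore the interval?** If the count runs over all cohorts, a suppressed event has at most 2 participants in total and cannot reach the Tier 2 threshold of 4. If it is per cohort or per comparison, Tier 2 may restore the interval when some other cohort reaches 4, and otherwise does not. Tier 3 and the special-interest table give frequencies. The forest plot might show the interval, but the text does not settle it.

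**The case against.** The case for leaving the SAP alone has several sound parts.

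- **Counts, percentages and differences stay visible**, and a reader can recompute the interval from them. This stands and keeps the severity low.
- **The rule's reach is narrow.** The CNS item is a whole SOC, and the ratio item also counts laboratory values, so both will probably exceed 2. This stands too: the rule mainly concerns the four ALT/AST preferred terms.
- **Liver safety has other displays.** SAP 15.2.5 plans shift tables, individual plots in multiples of ULN and an eDISH plot. These are useful, but none bounds the excess over Cohort 4.
- **The study is exploratory and all analyses are descriptive (Protocol 9.1).** True, but an interval is a descriptive quantity, and a plan without tests relies on intervals.

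A reader might also infer stronger points that the documents do not support.

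- *That the rule removes uncertainty at the counts that trigger a study hold.* Protocol 4.1 does act at low counts, for example when one or more "participants experience a serious study intervention-related CNS AE". But those criteria count graded, serious or related cases, whereas Tier 1 counts participants with any event in the row. One serious related CNS event may sit in a SOC row with many mild ones, and its interval is then displayed. The hold criteria act on cases and do not use this table.
- *That no upper bound would exist anywhere.* The exception is limited to the Tier 1 table. The forest plot carries no stated exclusion, and Tier 2 may supply an interval.
- *That the sponsor would read a missing interval as evidence of safety.* No passage says so.

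**Conclusion.** The point holds as a reporting matter of low severity. For sparse Tier 1 events the SAP prints a difference and omits its interval from the Tier 1 table, although its chosen method yields one. At 48 per cohort the omitted upper limits are 7.5, 11.0 and 14.0 points for 0, 1 and 2 events against none. No other table is certain to give them.

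The intervals rest on 48 treated per cohort; with 45 they are slightly wider. How often the rule would apply rests on assumed event rates and on how the count is read: with 5% in one cohort, 57% per cohort, or 26% or 10% over all cohorts with 1% or 2% elsewhere. No estimate, data collection or stopping decision changes.

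**What to change.** In SAP 15.1.2, delete the sentence that withholds the interval. State that the Miettinen-Nurminen 95% interval is displayed for every Tier 1 row at any count, including 0 v 0, and that the forest plot shows the same intervals. Deleting the sentence also removes the question of how participants are counted.

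Optionally, add an exact (Clopper-Pearson) upper limit for the incidence within each dose cohort. The two-sided 95% upper limits would be 7.4% for 0/48, 11.1% for 1/48 and 14.3% for 2/48.

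The cost is one sentence and a few table cells, with no new data or participants. The downside is that some wide intervals will be printed.
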